7.4. MAGNITUDE OF VIRAL SHEDDING

Objective: To test whether HCQ or HCQ + azithromycin is associated with decreased viral shedding from self-collected nasal swabs over 14 days compared to placebo

Outcomes: Quantity of SARS-CoV-2 detected from mid-nasal swabs by PCR as measured by cycle threshold (Ct)

Cohort: mITT Cohort

Data sets: VS Data Set

Analysis details: Generalized linear mixed effects models with random intercepts and slopes (time) will be used to model the quantity of SARS-CoV-2 over time. Because of the high number of samples where Ct was above the upper limit (eg >40) and not recorded, we will do analyses with Ct dichotomized as follows:

- Ct>40 on both targets vs Ct<=40 on either target
- Concordant results vs discordant or negative
- Ct<24 on either target as this may be an indicator of greater propensity to be infectious[2].

Fixed effects will include randomization arm, B-spline coefficients for time, an interaction between arm and time, cohort, age, and other baseline covariates indicated for the primary analysis. Time will be the time since enrollment visit to collection of the sample.

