
 • To test the efficacy of LPV/r compared to placebo to resolve COVID-19 symptoms within 14 days. 	
 • COVID-19 symptoms are based on the following criteria: 
 ○ At least TWO of the following symptoms: Fever ($\geq 38^{\circ}\text{C}$), chills, rigors, myalgia, headache, sore throat, new olfactory and taste disorder(s), OR ○ At least ONE of the following symptoms: cough, shortness of breath or difficulty breathing, OR ○ Severe respiratory illness with at least 1 of the following: 
 ▪ Clinical or radiological evidence of pneumonia, OR ▪ Acute respiratory distress syndrome (ARDS), OR ▪ LRTI, defined by resting $\text{SpO}_2 < 93\%$ sustained for 2 readings 2 hours apart AND presence of subjective dyspnea or cough 
Death or COVID-19-related hospitalizations will count as a failure to resolve symptoms.

 • To test the efficacy of LPV/r compared to placebo to reduce SARS-CoV-2 viral shedding 	
 • Time to clearance of nasal SARS-CoV-2, defined as 2 consecutive negative swabs (swabs collected daily Day 1 through Day 14)
Secondary	

 • To test the safety of LPV/r compared to placebo for treatment of high-risk outpatients with SARS-CoV-2 infection 	
 • Serious adverse events (including death and COVID-19-related hospitalization) and adverse events resulting in treatment discontinuation

 • To test whether LPV/r has an effect on the duration of hospitalization among persons who become hospitalized with COVID-19 disease 	
 • Days of COVID-19-related hospitalization

 • To test whether LPV/r has an effect on disease severity compared to placebo 	
 • Peak score on WHO Ordinal Scale for Clinical Improvement • Peak score on modified Flu-PRO within the first 14 days

 • To test whether LPV/r is associated with decreased viral shedding from self-collected nasal swabs over 14 days compared to placebo 	
 • Proportion of days with SARS-CoV-2 detected from mid-nasal swabs by PCR • Median quantity of SARS-CoV-2 detected from mid-nasal swabs by PCR

Exploratory
	

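### SAP 7.4 names viral quantity by Ct as its outcome but specifies only three yes/no analyses, so no difference in Ct or quantity is estimated

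*SAP*

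**What the plan says.** SAP 7.4 gives as its outcome the amount of virus on the mid-nasal swabs, with Ct as the measure, and states the model: "Generalized linear mixed effects models with random intercepts and slopes (time) will be used to model the quantity of SARS-CoV-2 over time". The next sentence changes what is modelled. "Because of the high number of samples where Ct was above the upper limit (eg >40) and not recorded", it continues, "we will do analyses with Ct dichotomized as follows". Three outcomes follow:

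- detection: "Ct>40 on both targets vs Ct<=40 on either target";
- two-target agreement: "Concordant results vs discordant or negative";
- Ct below 24 on either target, chosen as a possible marker of infectiousness.

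The fixed effects are arm, B-spline time, arm by time, cohort, age and the primary-analysis covariates. There are random intercepts and slopes.

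SAP Table 1 lists two endpoints for Secondary Objective 5: the proportion of days with virus detected, and the quantity detected. SAP 1.3 updates Secondary Objectives 2, 3 and 4 and does not mention Objective 5. SAP 8 adds descriptive summaries of vital signs, not of Ct. SAP 2 lists generic descriptive statistics for continuous variables without naming Ct.

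**The concern.** The stated endpoint and the specified analysis are different things. Each binary model gives an arm effect on the chance of crossing a threshold or of agreement between targets (an odds ratio if the link is logit, which the SAP does not say). None gives a difference in cycles. A reader of the results could learn whether swabs were more often negative, but not whether viral load was lower, which is what the objective asks.

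The stated reason does not require this. An unrecorded Ct above the limit is bounded below by the limit, so it is right-censored, and every recorded Ct at or below the limit remains usable. Under the first outcome Ct 25 and Ct 39 are the same result. Under the third, Ct 26 and no detection are the same result. Apart from whether a value is below 24, and whether the other target agreed, differences among recorded Ct values are discarded.

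**Working it through.** **Endpoint against analysis**

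| Place | Content |
|---|---|
| SAP Table 1, Objective 5 | Quantity is an endpoint |
| SAP 1.3 | Objective 5 not among the changes |
| SAP 7.4, outcome and model sentence | Quantity, by Ct, over time |
| SAP 7.4, analyses specified | Three binary outcomes |
| Rest of the SAP | No arm comparison of Ct or quantity |

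The mismatch needs no arithmetic and holds whatever the share of swabs above the limit.

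**Information kept by the Ct 40 cut, if Ct is one censored normal variable**

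SAP 7.4 states no power or effect size, so there is no figure to reproduce. The censored share c is not in the documents; 20% to 90% is assumed. With a = Φ⁻¹(1 − c), the information on a mean shift, in units of 1/SD² with SD treated as known and swabs as independent, is:

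- censored model: Φ(a) − aφ(a) + φ(a)²/(1 − Φ(a));
- yes/no at 40: φ(a)²/[Φ(a)(1 − Φ(a))].

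At c = 50%, a = 0 and φ(0)² = 0.159. The censored model has 0.5 + 0.159/0.5 = 0.818, the cut has 0.159/0.25 = 0.637, and the ratio is 0.78. The last column is Φ(2.80√ratio − 1.96), where 2.80 = 1.96 + 0.84.

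| Censored share | Censored model | Cut at 40 | Ratio | Power of the cut when the censored model has 80% |
|---|---|---|---|---|
| 20% | 0.956 | 0.490 | 0.51 | 52% |
| 30% | 0.921 | 0.576 | 0.63 | 60% |
| 50% | 0.818 | 0.637 | 0.78 | 70% |
| 70% | 0.655 | 0.576 | 0.88 | 75% |
| 90% | 0.359 | 0.342 | 0.95 | 78% |

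On the same basis the Ct 24 cut keeps 48% or less for SDs of 5 to 9.

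**Repeated swabs, still with no true clearance**

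This simulation assumed 70 per arm, 14 daily swabs, a slope of 1.3 cycles/day, person SDs of 5 (level) and 0.4/day (slope), residual SD 4, a 2.4-cycle shift and 300 replicates. It used pooled models with person-clustered errors. Starting Ct was 27, 31 or 35.

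| Censored share | Power: censored / Ct 40 / Ct 24 | Relative efficiency of Ct 40 |
|---|---|---|
| 34% | 69% / 62% / 52% | 0.83 |
| 52% | 67% / 62% / 37% | 0.91 |
| 69% | 61% / 59% / 12% | 1.03 |

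The loss at Ct 40 is smaller than under independence and disappears when censoring is heavy.

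**If some negative swabs are true clearance**

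SAP 1.5.2 assumes a median of 10 days to cessation with constant hazard. By Day 14, 1 − 2^(−14/10) = 62% have cleared, which matches Protocol 11.1.2. At the SAP's rate ratio of 1.6 it is 1 − 2^(−1.6 × 14/10) = 79%. Those swabs are not the tail of a normal Ct distribution.

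Two simulations (75 per arm and Ct trajectories assumed, pooled cluster-robust models) agree in direction. Run A used 400 replicates, a Monte Carlo SE of at most √(0.25/400) = 2.5 points.

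| Truth | Run A: power | Run B: power |
|---|---|---|
| No true clearance | Censored 62%; the two cuts 43% and 42% | Censored 51%, Ct 40 42%, Ct 24 35% |
| Arms differ only in clearance | Censored 46%, Ct 40 55% | Censored 41%, Ct 40 53% |
| Clearance ratio 1.6 plus 1 cycle | Censored 62%, Ct 40 64% | not run |
| 2-cycle shift, same clearance | Censored 22%, Ct 40 9%, Ct 24 30% | not run |

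In the clearance-only case (rate ratio 1.6 in run A) the censored model also reported a shift of about 2.8 cycles (run A) or 2.7 (run B), although Ct during shedding was the same in both arms.

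**The case against.** The SAP gives its reason openly, and Ct below 24 has a stated rationale. SAP 4.1.3 treats two consecutive negative swabs as clearance, so a model that reads every negative as an unseen high Ct conflicts with the trial's own view of the disease. The simulations bear this out: in each scenario with true clearance, one of the planned cuts matched or beat the censored model. Nor can a yes/no model at 40 verify the shape of the distribution beyond 40. All of this stands, and it limits both the claim and the remedy.

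A reader might infer more than the documents support:

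- **That the planned tests lose power, so a censored model should become the main test.** This holds only if negatives are the tail of one distribution. The censored share is not given, and the ranking can reverse.
- **That the detection outcome merely duplicates another analysis.** The SAP has no separate section for proportion of days detected. The Ct 40 model is its nearest analysis.
- **That all three outcomes are Ct cut-offs.** The second is agreement between targets.
- **That the SAP contradicts the protocol.** Protocol Section 4 does list "Median quantity of SARS-CoV-2 detected from mid-nasal swabs by PCR", but for the LPV/r comparison. This SAP covers the first three arms, so that line is context only.

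None of these points supplies the missing quantity estimate.

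**Conclusion.** The concern holds as a mismatch between endpoint and analysis. Quantity by Ct is the stated outcome, no specified analysis estimates a difference in it, and unrecorded values above the limit do not make that unavoidable. This conclusion rests on the text alone.

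The consequence for power is not settled. For a pure viral-load shift with no true clearance, the Ct 40 cut loses between about half the information (20% censored, independent swabs) and nothing visible (69% censored, repeated swabs). When treatment acts only through clearance, the Ct 40 cut does better than the censored model. These figures depend on assumed trajectories, sample sizes and censored shares, and the simulations used pooled rather than mixed models.

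The endpoint is secondary. The primary time-to-clearance analysis in SAP 4.1.3 does not depend on it.

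**What to change.** Keep the three binary models and add one quantitative analysis to SAP 7.4:

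1. **Response.** The lower Ct of the two targets, or one named target. State the actual assay limit, since the SAP gives 40 only as an example, and treat a swab above it as right-censored.
2. **Model.** A mixed model for censored Ct with the fixed and random effects already listed in 7.4. Handle household clustering as SAP 4.1 requires: robust standard errors or, if unavailable, a bootstrap (resampling households).
3. **Estimate.** Because arm interacts with spline time, name one contrast, such as the arm difference in cycles averaged over Days 2-14, with a 95% confidence interval.
4. **Two-part reading.** Report it beside the detection model and Ct among detected swabs. Say that the latter conditions on a post-randomization event, and that a censored-model shift accompanied by a detection effect but no difference among detected swabs may reflect clearance.
5. **Record.** Enter the addition in the SAP change history.

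The cost is SAP wording, one more model and a distributional assumption beyond the limit. No new data are needed. The gain is an estimate of the stated endpoint; a gain in power is not guaranteed.

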8. FOLLOW-UP SUMMARIES

Additional descriptive analyses will be performed on the following variables as recorded on participant surveys over time: Temperature, O₂ saturation, heart rate and respiratory rate. These analyses will include boxplots by visit and arm, further broken out by risk cohort and table reporting mean, median and IQR by visit and arm stratified by risk cohort.

10. CHANGE HISTORY

Major changes after Version 1.0 will be recorded here.

Version		Affected Section(s)	Activity Description
Number	Effective Date		
1.1	24/01/2022	Title Page	Corrected Protocol Registry Number
